### **7.3.3 Withdrawal of patients from treatment or study**

A patient should be withdrawn from the study treatment and discontinue the study for any one of the following reasons:

- ITI treatment is interrupted for >2 weeks
- Emergent or elective major surgery. Minor surgery such as tooth extraction or insertion/replacement of central venous access device is not a criterion for withdrawal.
- The patient received systemic treatment with chemotherapy and/or other immunosuppressant drugs. Use of corticosteroids for the treatment of asthma or management of acute allergic episodes is allowed with the exception of systemic corticosteroid treatment given to children daily or on alternate days at  $\geq 2$  mg/kg per day of prednisone or its equivalent or  $\geq 20$  mg/day if the duration is longer than 14 days.
- The patient is receiving concomitant immunomodulation.
- The patient is receiving emicizumab.
- The patient uses FVIII products other than rFVIIIFc (exception allowed for 1 emergency or accidental use).
- The patient or his legally authorized representative withdraws consent.
- If, in the clinical judgment of the investigator, it is not in the patient's best interest to continue with the study treatment.
- The patient enrolls into another interventional clinical study in which an investigational treatment or approved therapy for investigational use is administered.
- The patient is unwilling or unable to comply with the protocol.

The reason for the patient's withdrawal from the study must be recorded in the patient's case report form (CRF).

When a patient is withdrawn, the date of last rFVIIIFc dose and the date and reason for withdrawal (see above) should be clearly described in the relevant sections of the CRF. If a patient is removed from treatment because of an adverse event (AE), the reason for treatment withdrawal should always be stated as 'adverse event' irrespective of whether this was the investigator's or the patient's decision. The patients should be followed until the event has resolved, stabilized or returned to baseline.

The withdrawn patient should be examined, whenever possible, irrespective of the reason for withdrawal, as soon as possible. Relevant samples should be obtained and all relevant assessments should be completed, preferably according to the schedule for end of treatment visit. The CRF should be completed.

#### **7.3.4 Replacement of withdrawn patients**

Patients withdrawn prior to first dose will be replaced. Withdrawn patients who received at least one dose of rFVIIIFc will not be replaced.

### **7.4 Treatments**

#### **7.4.1 Identity of investigational medicinal products**

Possible deficiencies related to the handling and quality of rFVIIIFc should be reported to the study monitor and also directly to [[contact]](mailto:[contact]).

##### **7.4.1.1 Europe and Canada**

The investigational medicinal product rFVIIIFc is provided as a powder and solvent for solution for injection.

Each pack of rFVIIIFc contains 1 powder vial, 3 mL solvent in pre-filled syringe, 1 vial adapter, 1 infusion set, 2 alcohol swabs, 2 plasters and 1 gauze pad.

*Powder:*

The active substance is efmoroctocog alfa (recombinant coagulation factor VIII, Fc fusion protein). Each vial of rFVIIIFc contains nominally 250, 500, 1000, 2000 or 3000 IU efmoroctocog alfa.

The other ingredients are sucrose, sodium chloride, L-Histidine, calcium chloride dihydrate, polysorbate 20, sodium hydroxide and hydrochloric acid.

*Solvent:*

3 mL water for injections

The manufacturing of drug substance and drug product for the clinical study will not differ from the manufacturing of commercial available ELOCTA® and ELOCTATE® up to primary

packaging. Sobi will provide unlabeled rFVIIIFc drug product in its primary package to CRO who will package and label before distributing it to the study centers/designated local distributor.

Investigational medicinal product will be dispensed in accordance with national requirements. Home delivery of investigational medicinal product may be offered in compliance with national requirements.

rFVIIIFc should be stored and shipped refrigerated (2°C - 8°C) in the original pack. After dispensing, rFVIIIFc may be stored at room temperature (up to 30°C) for a single period not exceeding 6 months. After storage at room temperature, the product must not be put back in the refrigerator. rFVIIIFc should be stored at all times in the original pack in order to protect from light.

Once rFVIIIFc has been prepared it should be used immediately, or within 6 hours. The prepared solution should not be refrigerated and should be protected from direct sunlight. The prepared solution will be clear to slightly opalescent and colorless. Do not use the solution if it is cloudy or contains visible particles.

Labeling will comply with national regulatory requirements.

#### 7.4.1.2 USA

In USA, commercial available ELOCTATE® in different vial strengths, with auxiliary labeling for clinical trial use, will be used as rFVIIIFc supply.

Auxiliary labeling will include information regarding sponsor name and contact details, clinical study number, kit number and patient number. 'For clinical trial use only' and 'Keep out of reach of children' will also be included.

ELOCTATE® is supplied in kits comprising a single use vial containing nominally 250, 500, 1000, 2000, or 3000 IU, a pre-filled syringe with 3 mL sterile water for injection, and a sterile vial adapter. Sites will be supplied with infusion sets, alcohol swabs, plasters and gauze pads separately.

ELOCTATE® should be stored and shipped refrigerated (2°C - 8°C/36°F-46°F) in the original pack. After dispensing, ELOCTATE® may be stored at room temperature (up to 30°C/86°F) for a single period not exceeding 6 months. After storage at room temperature, the product must not be put back in the refrigerator. ELOCTATE® should be stored at all times in the original pack in order to protect from light.

The reconstituted product may be stored at room temperature, not to exceed 30°C (86°F), for up to 3 hours. Protect from direct sunlight. After reconstitution, if the product is not used within 3 hours, it must be discarded. Do not use ELOCTATE® if the reconstituted solution is cloudy or has particulate matter.

Investigational medicinal product will be dispensed in accordance with national requirements. Home delivery of investigational medicinal product may be offered in compliance with national requirements.

#### 7.4.2 Selection of doses

Refer to Section 7.2.2 for the rationale for the selected dosage regimen, dose levels and treatment duration.

During the ITI period the initial rFVIIIFc dose administered is 200 IU/kg/day, which may be given as once daily doses, or divided in two doses per day. If FVIII:C levels raise above 200 IU/dL already at a low-titer inhibitor (< 5 BU/mL), and before all three tolerance criteria have been confirmed, the dose should be decreased according to investigator judgment to maintain the peak FVIII:C levels between 100-200 IU/dL.

During the initial part of the tapering period the rFVIIIFc dose administered should be adjusted according to investigator judgment based on the FVIII:C results to maintain the peak FVIII:C levels between 100-200 IU/dL, with an aim to taper the FVIII:C levels to reach prophylactic levels as judged by the investigator after 16 weeks. Examples of different tapering approaches are provided in the pharmacy manual. FVIII:C levels should be  $\geq 1$  IU/dL at all time points during the tapering period. The duration of the tapering period may be adjusted after approval by the sponsor's medical director however the dose should be decreased over at least 16 weeks.

During the follow-up period, the prophylaxis regimen should be adjusted based on clinical response, and with an aim to keep FVIII:C levels  $\geq 1$  IU/dL at all time points according to investigator judgment and local practice.

The patients should be instructed not to take a double dose to compensate a forgotten dose; instead, the next dose of rFVIIIFc should be taken on schedule the next day or according to the instructions of the investigator.

Bleeding episodes occurring during the ITI period should be treated according to investigator judgment and local practice. The use of bypassing agents such as aPCC and rFVIIa will be allowed but patients should be instructed to contact the investigator. Prescription of bypassing agents should be according to investigator's judgment and local practice and if not in accordance with local label the medical monitor is to be notified and the rationale documented. The prophylactic prescription of bypassing agents requires notification by the investigator to the medical monitor and documentation of rationale.

Bleeding episodes in patients with low-titer inhibitors (<5 BU/mL) during the ITI period where the investigator judge that rFVIIIFc can provide sufficient hemostatic control, as well as in patients during the tapering and follow-up period should be treated with rFVIIIFc, with doses according to investigator judgment and local practice. In specific situations, e.g. if bleeding is unresponsive to treatment with rFVIIIFc, treatment with bypassing agents may be considered, as judged by the investigator. Such use is to be notified to the medical monitor and the rational documented in the medical records.

After the end of treatment visit, the patient should be treated according to investigator judgment and local practice. No further investigational medicinal product will be provided.

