### 7.1.2 ITI period

The first dose of rFVIIIFc will be administered at the baseline visit and the ITI treatment will continue until ITI success or failure is declared, or for a maximum of 60 weeks. The ITI regimen

consists of daily administration of rFVIIIFc (200 IU/kg per day), which may be given as once daily injection or divided in two injections per day at the discretion of the investigator.

Visits will occur 2 and 4 weeks after the baseline visit and then every 4th week. For patients who achieves an IR >66% of the expected IR for each specific patient as per investigator judgment, the visit frequency will be changed to every other week.

During the ITI period patients will undergo procedures and assessments as per the schedule of events (Table 1). Samples for inhibitor testing and assessment of FVIII:C levels will be analyzed at the local laboratory as well as centrally. The results from the local laboratory will constitute the primary data of the study to be used for statistical analysis.

At each visit the inhibitor titer will be assessed. If, after the initial 3 months, a downward trend of at least 20% in the inhibitor titer in any 6-month period is not seen, the patients should be regarded as a treatment failure and complete the end of treatment visit as soon as possible.

The assessment of ITI outcome is illustrated in Figure 2. Once a patient has demonstrated negative inhibitor (<0.6 BU/mL) at two consecutive visits, evaluation of IR will be performed at the next visit. When an IR >66% of the expected IR has been obtained at 2 consecutive visits, pharmacokinetic assessments to determine half-life will be performed at the subsequent visits until a half-life of  $\geq 7$  hours is attained. Patients are required to have at least a 24-hour washout prior to the half-life assessment.

An unscheduled visit after the 60-week period may be scheduled to allow the patient to get a confirmatory test, as long as the first test occurred during the 60-week period. If the second test confirms the results of the first test, the date of ITI outcome is the date of the first value, which occurred during the 60-week period. Fluctuations in inhibitor levels is common and variability in inhibitor titer is expected. Patients will be evaluated on a case-by-case basis.

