#### **7.4.3.2 Dose calculations**

The nominal strength is defined as the target potency of the vial (that is, 250 IU, 500 IU, 1000 IU, 2000 IU, or 3000 IU per vial). Nominal strength will be used for all calculations of rFVIIIFc dose and whole vials will be used to achieve the target dose, rounded to the nearest 250 IU. Per investigator judgment, it is also allowed to round up to the nearest 500 IU to decrease the number of vials used per injection.

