**PAREXEL International**  
**Statistical Analysis Plan**

**6.1.2      Exposure and Compliance**

**6.1.2.1    Treatment Regimen**

For each treatment regimen, including the initial regimen and subsequent changes, the following will be recorded in the CRF:

- Start and stop date of regimen
- Status (ongoing or stopped)
- Dose (IU/kg) and dosing frequency
- Reason for regimen change (initiation of ITI, tapering of dose, entering follow-up period, decrease due to high activity levels, dose increase due to low activity levels, other).

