**6.3.13.10 Adherence**

Adherence will be calculated in two ways as follows:

- Dose adherence: dose administered as registered in diary / doses prescribed
- Frequency adherence: number of days with infusions as registered in the diary / number of days on which infusion was prescribed

Dose prescribed will be taken from the CRF. The frequency as entered in the CRF will also be used for the calculation of number of days on which dose was prescribed.

The number of doses administered will be calculated from the data entered into the eDiary and the eCRF.

This calculation will be done for each period, and the results will be listed and summarized descriptively using the respective period specific analysis set. For the calculation of dose adherence also see also Section 6.3.14 on the handling of doses recorded in duplicate (entered in both subject diary and CRF).

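### Frequency adherence counts days, so on a permitted twice-daily regimen it cannot register a missed second injection; the SAP also leaves open whether dose adherence is an amount or a count.

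*Protocol*

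**What the plan says.** **Dosing.** Protocol 7.4.2 states: "During the ITI period the initial rFVIIIFc dose administered is 200 IU/kg/day". On how that daily amount is divided, the same sentence adds: "which may be given as once daily doses, or divided in two doses per day". Protocol 7.1.2 also allows two injections a day, at the investigator's discretion, and continues ITI until an outcome is declared "or for a maximum of 60 weeks".

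**Vial rounding.** Under Protocol 7.4.3.2, "whole vials will be used to achieve the target dose, rounded to the nearest 250 IU". It adds: "Per investigator judgment, it is also allowed to round up to the nearest 500 IU to decrease the number of vials used per injection".

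**Adherence.** SAP 6.3.13.10 has two measures:
- "Frequency adherence: number of days with infusions as registered in the diary / number of days on which infusion was prescribed"
- "Dose adherence: dose administered as registered in diary / doses prescribed"

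Protocol 9.3.4.10 defines both in the same way. The SAP takes the prescribed dose and frequency from the CRF, where the regimen is recorded as "Dose (IU/kg) and dosing frequency" (SAP 6.1.2.1). Administrations are recorded as total nominal IU (SAP 6.1.2.2). The same SAP section then speaks of calculating the number of doses administered, which reads as a count.

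**The concern.** Describing adherence is a stated objective and adherence is a named secondary endpoint (Protocol 6.2 and 6.2.1). In a single-arm study of 20 patients, a reader will use it to judge whether patients received the regimen whose outcome is being described.

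A frequency measure should fall when injections are missed. Here the unit of treatment can be half a day's dose, while the unit of measurement is a whole day with any infusion. The SAP is aware of twice-daily regimens: its rule for duplicate dosing entries (6.3.14) is built so that morning and evening doses are not taken for duplicates. The adherence section was not aligned with that.

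The dose measure has a different gap. The numerator wording suggests an amount in one place and a count in another. If it is an amount, nothing says which body weight converts IU/kg to IU, or whether the denominator is the target dose before or after vial rounding. Two programmers could follow the text and report different results.

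**Working it through.** The documents state no adherence figure, so there is none to reproduce. The check applies the SAP's two ratios to regimens the protocol allows.

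**1. Frequency adherence**

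Inputs: two injections a day (Protocol 7.4.2); maximum ITI period 60 weeks (Protocol 7.1.2).

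- Prescribed days = 60 × 7 = 420.
- Prescribed injections = 420 × 2 = 840.
- SAP frequency adherence = days with any infusion / 420.
- Injection-based adherence = injections given / 840.

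| Days with one of two injections missed | Injections given | SAP frequency measure | Injection-based |
|---|---|---|---|
| 42 | 798 | 420/420 = 100% | 95% |
| 210 | 630 | 420/420 = 100% | 75% |
| 420 | 420 | 420/420 = 100% | 50% |

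No assumption about body weight or how the dose is split enters this result.

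**2. Dose adherence, if read as a count**

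Rounding plays no part, and every missed injection lowers the ratio. The patient in the last row scores 420/840 = 50%.

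**3. Dose adherence, if read as an amount with an unrounded denominator**

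Assumptions, because the documents do not settle them: the daily dose is split equally (100 IU/kg per injection), and the CRF dose is the target before rounding. Ratio for a fully adherent patient = rounded dose / target.

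Example at 15.1 kg, target 1510 IU per injection:
- Nearest 250 IU: 1500 IU (1000 + 500, two vials), ratio 1500/1510 = 99.3%.
- Up to 500 IU: 2000 IU (one vial), ratio 2000/1510 = 132%. Here rounding up does save a vial.
- At 2000 IU, the share of injections that could be missed with the ratio still at 100% is 1 − 1510/2000 = 24.5%.
- If every second injection is missed, the ratio is 2000/(2 × 1510) = 66.2%, or 1500/(2 × 1510) = 49.7% under nearest-250 rounding.

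Mean ratio over 10 to 30 kg in 0.1 kg steps, with vials of 250, 500, 1000, 2000 and 3000 IU (Protocol 7.4.1):

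| IU/kg per injection | Nearest 250 IU | Up to 500 IU only where that saves a vial, otherwise nearest 250 IU |
|---|---|---|
| 200 | 100.0% | 102.7% |
| 100 | 99.9% | 105.9% |
| 50 (assumed) | 99.9% | 108.3% |

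Rounding up saves a vial at about 25% to 37% of these weights. The weight range is itself an assumption; the protocol admits any age and gives no weights.

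**The case against.** **Adherence is deliberately measured in two ways.** This largely stands for gross omission. The patient who misses every second injection scores 50% on dose adherence read as a count, or roughly half to two thirds read as an amount (49.7% or 66.2% at 15.1 kg), so the summary as a whole would not conceal it. But the measure named frequency adherence still reads 100%, and its companion has no settled unit.

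**The rounding criticism depends on a reading the SAP partly points away from.** This also stands. The reference to a number of doses supports a count, on which rounding has no effect. No section says that the CRF dose is the unrounded target. What can be said is that the unit is undefined, not that the formula certainly mis-scores.

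**A stronger reading is tempting.** A reader might infer that both formulas let missed injections show as 100% or more, with large inflation in small children. For instance, an 11 kg child with a 1100 IU target who is given 1500 IU would score 136%. The documents do not support this. Missed doses cannot take the day-based ratio above 100% under daily dosing. The option to round up exists to reduce the number of vials, and at 11 kg it would raise the number from one (1000 IU) to two (1000 + 500 IU). Rounding up at every weight would give means of 106.7%, 114.0% and 129.6% for the three doses tabulated. Restricting it to its stated purpose brings these down to 102.7%, 105.9% and 108.3%.

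**Adherence carries little weight in the plan.** It is descriptive, is not among the prognostic factors in SAP 6.3.12.1, and every dose is listed. This limits the consequence but does not correct the definition.

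**Conclusion.** The frequency point holds without conditions: for a twice-daily regimen the measure stays at 100% while up to 420 of 840 injections are missed, provided one is given each day. How many patients this touches depends on how many use two injections a day, which the documents do not give.

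The dose-adherence point is a gap in specification. Its numerical effect arises only if the measure is an amount with an unrounded denominator. Even then it is large only at isolated weights (132% at 15.1 kg, equal split assumed). Nearest-250 rounding averages about 100%, and rounding up only where it saves a vial averages about 103% to 108% at 10 to 30 kg; the upper figure rests on an assumed 50 IU/kg per injection.

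The primary endpoint and the ITI outcome classification are unaffected. The change is worth making because the endpoint is named and the correction is simple.

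**What to change.** In SAP 6.3.13.10:

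1. Define frequency adherence as planned injections given divided by planned injections prescribed, with two per day for twice-daily regimens. Exclude injections given for bleeds, using the recorded reason for injection. The day-based figure may be kept as a supplement, which also preserves the definition in Protocol 9.3.4.10.
2. Define dose adherence as nominal IU given divided by nominal IU prescribed. The denominator should be the single whole-vial amount the patient was instructed to take, after the rounding in Protocol 7.4.3.2. It should not be the unrounded IU/kg target. Nor should either of two permitted amounts count as full adherence, because a patient told to take the larger amount who takes the smaller would then score 100%. Fixing this measure as an amount also keeps it distinct from the injection count in item 1.

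This changes only the analysis, not any dose or rounding rule. Body weight, prescribed frequency, nominal IU and reason for injection are already collected. SAP 6.1.2.1 lists the prescribed dose in IU/kg only, so where the instructed whole-vial amount was not recorded it would have to come from site records or be derived, and the SAP should say which. Otherwise the cost is minor wording and programming, and some adherence figures may be less favourable.

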### **7.4.3 Selection and timing of doses for each patient**

#### **7.4.3.1 Administration of rFVIIIFc**

After dissolving the powder for injection with the solvent supplied in the pre-filled syringe, rFVIIIFc will be delivered via a slow push IV injection over several minutes, at a rate of administration determined by the patient's comfort level.

As a precautionary measure, the initial administration of rFVIIIFc should be performed under medical observation, where proper medical care for allergic reactions could be provided. Patients/caregivers will be instructed to administer subsequent rFVIIIFc doses at home with the exception of the dose given in conjunction with study visits.

The patient/caregiver must enter dosing information on rFVIIIFc and/or FVIII bypassing agents into the diary as soon as possible after an injection, to ensure data integrity, and to facilitate appropriate medical review and dosing guidance. It is recommended that patients/caregivers enter dosing information immediately after an injection.

Complete instructions for the preparation and administration of rFVIIIFc are provided in the pharmacy manual and the patient information.

#### **7.4.3.2 Dose calculations**

The nominal strength is defined as the target potency of the vial (that is, 250 IU, 500 IU, 1000 IU, 2000 IU, or 3000 IU per vial). Nominal strength will be used for all calculations of rFVIIIFc dose and whole vials will be used to achieve the target dose, rounded to the nearest 250 IU. Per investigator judgment, it is also allowed to round up to the nearest 500 IU to decrease the number of vials used per injection.

